2.0 Revision

Page 2 of 31

#### **Version History** 1.

Version	Summary of Changes	Author(s)/Title
1.0 23 APR 2024	Not Applicable, New Document	/ Sr Statistician
2.0 22 JUL 2024	
 
Par 7.1.3:
 
Updated the Per Protocol population set definition to exclude participants with major protocol deviations, including now non-compliance with randomization assignment
 
Added definition and sensitivity purpose of "As Treated population set" for continuation phase
 
Par 7.10:
 
Specified that safety reporting will be performed by both assigned randomization treatment and actual treatment received
 
	Prin Statistician

#### List of Abbreviations and Definitions of Terms 2.

Abbreviations		
ADE	Adverse Device Effect	
AE	Adverse Event	
AHCL	Advanced Hybrid Closed Loop	
AIT	Active Insulin Time	
BG	Blood Glucose	
BMI	Body Mass Index	
CGM	Continuous Glucose Monitoring	
CIP	Clinical Investigation Plan	
CRF	Case Report Form	
CSII	Continuous Subcutaneous Insulin Infusion	
CV	Coefficient of Variation	
DD	Device Deficiency	
DKA	Diabetic Ketoacidosis	
EDC	Electronic Data Capture	
HbA1c	Glycosylated hemoglobin	
ICF	Informed Consent Form	
ITT	Intention to Treat	

Form

Revision 2.0

Page 4 of 31

Medtronic

Abbreviations		
MDI	Multiple Daily Injections	
MedDRA	Medical Dictionary for Regulatory Activities	
PP	Per Protocol	
SADE	Serious Adverse Device Effect	
SAE	Serious Adverse Event	
SAP	Sensor Augmented Pump	
SBL	Suspend Before Low	
SD	Standard Deviation	
SG	Sensor Glucose	
SMBG	Self-Monitoring of Blood Glucose	
TAR	Time above Range	
TBR	Time below Range	
T1D	Type 1 diabetes	
TDD	Total Daily Dose	
TIR	Time in Range	
USADE	Unanticipated Serious Adverse Device Effect	

#### 3. Introduction

The global incidence of newly diagnosed cases of type 1 diabetes (T1D) in children and adolescents is increasing. In 2019, the International Diabetes Federation (IDF) indicated that every year, 98,200 children and adolescents aged 0–14 years are diagnosed with T1D worldwide .

In T1D, glycemic control is influenced by numerous factors, such as insulin dosage, insulin absorption, timing, physiological/lifestyle factors such as exercise, food intake, hormones, and illness. The use of sensor-augmented pump therapy with predictive low-glucose suspend features, available in the commercialized MiniMed 640G System, in which the pump stops insulin delivery when an algorithm predicts glucose levels to drop below the prespecified low-glucose threshold, is accompanied by improvements in glycemic control in children, but the management of the therapy remains challenging in the young children due to high variability of insulin requirements, marked insulin sensitivity and unpredictable eating and activity patterns.

In 2020, a sensor-augmented pump system, called the MiniMed 780G system, with an advanced hybrid closed loop (AHCL) algorithm became commercially available in Europe. The system features SmartGuard technology which allows the pump to automatically adjust the amount of insulin delivered based on sensor glucose (SG) readings. The system can also automatically deliver correction boluses and has multiple adjustable glucose targets (100 mg/dL, 110mg/dL, 120 mg/dL and 150 mg/dL) (5.5 mmol/L, 6.1 mmol/L, 6.7 mmol/L and 8.3 mmol/L).

Several studies have been completed and are ongoing on the AHCL MiniMed 780G system to demonstrate its safety and effectiveness in children, adolescents, and adults. In a pivotal study, it was demonstrated

CIP342 LENNY Statistical Analysis Plan	Form
Revision 2.0 Page 5 of 31	Medtronic

that the MiniMed 780G system helped children over 7 years old to reach better time in range (TIR) and better mealtime glycaemia without increasing time below range (TBR), severe hypoglycemia or ketoacidosis. Furthermore, real-life data analysis in 3,211 users, reporting age <15, demonstrated a GMI of 6.8±0.3%, TIR of 73.9±8.7%, and TBR (70 mg%) of 3.2%, while spending 92.7% of time in AHCL . These studies and real-life usage of the MiniMed 780G system has been shown to improve glycemic control and reduce the burden of management of T1D in children and adolescents. However, studies involving very young children remain limited, and therefore this randomized trial is being conducted to evaluate safe usage of the MiniMed 780G system in comparison with the currently available standard sensor-augmented pump therapy for young children 2 to 6 years old.

This Statistical Analysis Plan (SAP) Version is based on Protocol E 3' OCT 2023, and it has been designed to document, before data is analyzed, the planned statistical analyses for both study and continuation phases and will be used to support the clinical reports. This SAP does not limit the analysis in reports, and additional analyses of the study data beyond this plan might be conducted. However, this document provides the basis for the statistical sections of the clinical reports. Analyses not planned in the SAP and incorporated into the final report will be referred to as "not prespecified". Moreover, in case any analyses will be done differently than planned in the CIP or SAP, an explanation will be provided in the final reports.

## 4. Study Objectives

## 4.1 Primary Objective

The objective of the study is to evaluate the safety and performance of the MiniMed™ 780G system in Auto Mode firstly in comparison to the MiniMed™ 780G system in Manual Mode with Suspend before low activated (currently available standard therapy) in the study phase and secondly in comparison to the new MiniMed™ 780G BLE 2.0 system with DS5 sensor in Auto Mode among paediatric population (2-6 years old) in the continuation phase.

#### 4.1.1 Study Phase Primary Endpoint

The primary endpoint for LENNY study phase is the between-treatment difference (MiniMed™ 780G system in Auto Mode vs MiniMed™ 780G system in Manual Mode) in the percentage of time that the sensor glucose measurement is in the target range, 70 to 180 mg/dL (3.9-10.0 mmol/L) during the study phase period. This endpoint will be assessed for non-inferiority with an absolute margin of 7.5% TIR.

#### 4.1.2 Continuation Phase Primary Endpoint

The primary endpoint for LENNY continuation phase is the between-treatment difference (MiniMed™ 780G BLE 2.0 system with DS5 in Auto Mode vs MiniMed™ 780G system in Auto Mode) in the mean HbA1c

CIP342 LENNY Statistical Ana	l ysis Pla n		Form
Revision	2.0	Page 6 of 31	Medtronic

(%) at the end of 12-week continuation phase period 2. This endpoint will be assessed for non-inferiority with an absolute margin of 0.4% HbA1c.

# 4.2 Secondary Endpoints

#### 4.2.1 Study Phase Secondary Endpoint

The secondary endpoints for LENNY study phase will be the between-treatment (MiniMed™ 780G system in Auto Mode vs MiniMed™ 780G system in Manual Mode) difference in the study phase for:

- Mean HbA1c at the end of each 12-week period, non-inferiority test with an absolute margin of 0.4% HbA1c.
- % Time spent in target range (70 to 180 mg/dL [3.9-10.0 mmol/L]), simple superiority test.
- Mean HbA1c at the end of each 12-week period, simple superiority test. •

#### 4.2.2 Continuation Phase Secondary Endpoint

The secondary endpoints for LENNY continuation phase will be the between-treatment (MiniMed™ 780G BLE 2.0 system with DS5 in Auto Mode vs MiniMed™ 780G system in Auto Mode) difference in the continuation phase period 2 for:

- Mean HbA1c at the end of the 12-week continuation phase period 2, simple superiority test.
- % Time spent in target range (70 to 180 mg/dL [3.9-10.0 mmol/L]) during continuation phase period 2, non-inferiority test with an absolute margin of 7.5% time in range.
- % Time spent in target range (70 to 180 mg/dL [3.9-10.0 mmol/L]) during continuation phase period 2, simple superiority test.

# 4.3 Safety Endpoints

The following safety endpoints will be assessed for each treatment during each 12-week period in both the study phase and continuation phase:

- Number of severe hypoglycemic events
- Number of Diabetic Ketoacidosis events (DKA)
- Number of Serious Adverse Events (SAEs)
- Number of Serious Adverse Device Events (SADEs)
- Number of Unanticipated Serious Adverse Device Events (USADEs)
- Number of Device Deficiencies for each treatment during each 12-week period in the Study Phase

# CIP342 LENNY Statistical Analysis Plan Form Revision 2.0 Page 9 of 31 Mectronic

## 5. Investigation Plan

This study is a pre-market, prospective, open-label, multi-center, randomized crossover trial in paediatric subjects (2-6 years old) with type 1 diabetes. The study consists of a run-in phase, a study phase, and a continuation phase (**Figure 1**).

Figure 1 - Study Design - CIP version E

#### Study Phase - Run-in Phase:

The purpose of the run-in phase (2 to 4 weeks) is to train the subject's parent(s)/legal guardian(s) on the MiniMed 780G system in Manual Mode with Suspend before low activated and to collect 2 weeks of baseline data.

At the end of Run-in Phase, subjects will be randomized into 2 sequences (A and B).

Successful completion of run-in phase requires sensor usage  $\geq$ 70% over the previous 2 weeks during the run-in phase. If this is not achieved (e.g. sensor felt off) the run-in phase can be extended for another 7 to 14 days to achieve sensor usage  $\geq$ 70%.

#### Study Phase:

During the study phase, each sequence consists of 2 phases of 12 weeks each separated by a 2-week washout phase for a total of 26 weeks.

- Sequence A: subjects will start using the MiniMed 780G system in Auto Mode for 12 weeks (Treatment). The washout phase of 2 weeks will be followed by a 12-week phase where subjects will use 780G system in Manual Mode with SBL activated (Control).
- Sequence B: subjects will continue to use MiniMed 780G system in Manual Mode with SBL activated for 12 weeks (Control). After a washout phase of 2 weeks, subjects will start to use the MiniMed 780G system in Auto Mode for a 12-week phase (Treatment).

During the washout period all the subjects will use MiniMed 780G system in Manual Mode with SBL activated.

#### **Continuation Phase (Visit 12-15):**

For the duration of the continuation phase, enrolled subjects will enter the continuation phase period 1 and will use MiniMed 780G system in Auto Mode.

At the end of the continuation phase period 1, subjects will be randomized into 2 arms (A2 and B2) and enter period 2 for 12 weeks.

- Arm A2: Subjects will start using the MiniMed™ 780G BLE 2.0 system with the DS5 sensor for 12 weeks
- Arm B2: Subjects will continue to use MiniMed™ 780G system in Auto Mode for 12 weeks

Based on interim analysis results, enrollment may be re-opened only for the Continuation phase, and the newly enrolled patients will have a dedicated run-in 2.

#### **Continuation Phase - Run-in 2 Phase:**

The purpose of the run-in 2 phase (3 to 10 days) is to train the newly enrolled subject's parent(s)/legal guardian(s) on the MiniMed 780G system in Manual Mode with Suspend before low activated. At the end on the continuation phase run-in 2 period, subjects will start using the 780G system in Auto Mode.

This document is electronically controlled

CIP342 LENNY Statistical Analysis Plan	Form
Revision 2.0 Page 11 of 31	Medtronic

## 7. Statistical Methods

## 7.1 Study Subjects

#### 7.1.1 Disposition of Subjects

A subject is enrolled in the study when he/she signs and dates the Patient Informed Consent.

For study phase a summary of number of subjects enrolled, entered the run-in phase, randomized, and completed (by study sequence and study period), screen failures and drop-outs will be reported.

For continuation phase a summary of number of subjects enrolled, entered the continuation phase period 1, randomized, and completed the continuation phase period 2 (by study arm), and drop-outs will be reported.

For both study and continuation phases, a listing of subjects that failed to meet randomization criteria, screen failures and drop-out with the corresponding reasons will also be reported, separately.

Two consort flow diagrams similar to figure 2 and figure 3 will be created to describe patient disposition in study and continuation phase, respectively.

Figure 2 – Patients disposition flowchart -study phase

Rev C

Figure 3 – Patients disposition flowchart -continuation phase

#### 7.1.2 Clinical Investigation Plan (CIP) Deviations

Deviations from the clinical investigation plan will be collected as deviations on the Study Deviation eCRF. Deviations will be summarized in the final report in a table by category. The number of deviations per category, the number, and percentage of subjects with a deviation in each category will be reported. Listing of deviations, including reason for deviation, will be reported.

#### 7.1.3 Analysis Sets

The following subject sets will be used for the analysis:

#### • Intention to Treat (ITT) Population:

For the study phase, the ITT population will include all randomized subjects for that phase, and for the continuation phase, the ITT population will include all randomized subjects for that phase. These subjects will be assessed and analyzed as members of the intended period/treatment, irrespective of their compliance to the planned course of treatment or deviations from protocol. For the primary, secondary, and exploratory endpoints, efficacy analyses will be performed in the Intent to Treat (ITT) basis.

# CIP342 LENNY Statistical Analysis Plan Form Revision 2.0 Page 14 of 31 Medtronic • Per Protocol (PP) Population:

For both, study phase and continuation phase, the PP population will include all randomized subjects in the respective phase, and excluding any subject with at least one of the following deviations (to be assessed independently in each phase):

- Auto Mode use during is less than 75%
- Sensor use is less than 70%
- o Subject did not complete the specific phase, respectively
- Subject did not meet screening criteria for the specific phase but continued the phase
- Subject did not meet randomization criteria for the specific phase but continued the phase
- o Subject not compliant with the assigned randomization treatment

For sensitivity purposes, efficacy analysis of the primary and secondary endpoints will also be performed in the Per Protocol set.

The criteria listed above will be assessed separately for study and continuation phase, respectively, and separate ITT and PP population sets will be defined accordingly.

#### • As Treated (AT) Population:

For the continuation phase, the AT population will include all randomized subjects for that phase. These subjects will be assessed and analyzed as members of the actual treatment. For sensitivity purposes, efficacy analysis of the primary and secondary endpoints will also be performed in the As Treated set.

#### • Safety Population

The Safety Population will include all subjects with signed inform consent.

#### 7.2 General Methodology

Summary statistics for Continuous variables will be represented by number of subjects(n), mean, median, standard deviation, minimum and maximum and categorical variables will be represented by counts and percentages. P-values for hypothesis testing will be evaluated based on two-sided testing using significance level of 0.05. Confidence intervals will be reported as two-sided 95% confidence intervals. Normality will be verified by appropriate statistical methodology.

#### Time windows for device data metrics will be defined as follow:

Revision 2.0 Page 15 of 31

- Run-in period: from Visit 2 (excluded) to Visit 3 (excluded); •
- Study phase period 1: from Visit 3 (excluded) to Visit 7 (excluded); •
- Washout period: from Visit 7 (excluded) to Visit 8 (excluded);
- Study phase period 2: from Visit 8 (excluded) to Visit 11 (excluded); ٠
- (in case of newly enrolled subjects) Run-in 2 period: from Visit 2A (excluded) to Visit 3A ٠ (excluded);
- Continuation phase period 1: from Visit 11 (excluded) to Visit 13 (excluded); ٠
- Continuation phase period 2: from Visit 13 (excluded) on.

CGM data from the day of the visits will not be included in the device data metrics calculation to avoid any possible bias due to the change in the treatment and settings.

Time windows for safety events will be defined as follow:

- Pre-Run-in period: from ICF signature date (included) to Visit 2 (excluded)
- Run-in period: from Visit 2 (included) to Visit 3 (excluded); •
- Study phase period 1: from Visit 3 (included) to Visit 7 (included); •
- Washout period: from Visit 7 (excluded) to Visit 8 (excluded); •
- Study phase period 2: from Visit 8 (included) to Visit 11 (excluded); •
- (in case of newly enrolled subjects) Pre-Run-in 2 period: from ICF signature date/Visit 1A • (included) to Visit 2A (excluded)
- (in case of newly enrolled subjects) Run-in 2 period: from Visit 2A (included) to Visit 3A (excluded);
- Continuation phase period 1: from Visit 11 (included) to Visit 13 (excluded);
- Continuation phase period 2: from Visit 13 (included) on. •

The templates for Tables, Listings and Figures (TLFs) will be available in the TLFs document for both study and continuation phase.

It is anticipated that SAS 9.4 or later (SAS Institute Inc., Cary, NC, USA) will be used to perform all statistical analyses.

Additional exploratory analyses will be conducted as deemed appropriate and described as ad-hoc analysis in the study report.

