9.1 Schedule of Events

Subjects may participate in up to 15 planned study visits, as presented in **Figure 10**. A remote office visit (audio visual) may be performed for office visits in cases where an office visit is not possible.

Figure 10. Visit Schedule

Prior to study start, Investigator or authorized designee must obtain written informed consent from the parents/legal guardian before any clinical study related activity (including screening) takes place and document informed consent process in the medical chart of the subject (Visit 1).

Subject enrolled will start the Run-in phase. During Run-in phase MiniMed 780G -system training program will be provided, including e.g. infusion set insertions/replacements, meal bolus procedure, what to do with significant illness, how to react on safety/alert notifications, when to perform BG measurements and when to contact site staff with the contact information provided.

During Run-in Phase subject will use 780G system in Manual Mode + SBL set at 65 mg/dL (3.6 mmol/L) (standard of care therapy- Visit 2). Study staff will conduct at the minimum a subject visit, 2 weeks

after Manual Mode + SBL has been started (Visit 3). Additional phone contacts or visits may be conducted (unscheduled visits), as needed.

Eligible subjects must successfully complete the run-in phase by demonstrating tolerance to sensor wear and sensor usage \geq 70% in the last 2 weeks before being randomized. If this is not achieved (e.g. sensor felt off) the run-in phase can be extended for another 7 to 14 days.

Subject randomized in Sequence A will be trained on the use of MiniMed 780G system in Auto Mode (Visit 3A) and they will start to use the system with follow up visits at 2 weeks (Visit 4), 4 weeks (Visit 5) 8 weeks (Visit 6) and 12 weeks (Visit 7) after Auto mode Start.

At 12 weeks (Visit 7) subjects will stop Auto Mode and will start using the system in Manual Mode + SBL set at 65 mg/dL (3.6 mmol/L) for the washout period.

Following the end washout period (Visit 8), follow up visits will be done respectively every 4 weeks (Visit 9, 10 and 11). Additional phone contacts or visits may be conducted (unscheduled visits), as needed.

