- Perform blood sample collection for creatinine clearance at local lab. If creatinine clearance test was performed ≤ 6 months prior to screening, only confirm date of collection at local lab and creatinine clearance value in medical chart. *Note: Creatinine clearance threshold for exclusion* < 30 mL/min and must be calculated with the Cockcroft, CKD-EPI or MDRD equations. The sites will follow routine practice for evaluation of the creatinine clearance.
- $_{\odot}$ $\,$ Perform blood sample collection for HbA1c at the Local Lab.
- \circ $\,$ Collect number of DKA in the last 3 months.

Run-In Phase:

Visit 2* (Office/Remote): Start Manual Mode + SBL [Visit 1 + 0-3 days (Window + 5 days)]

Note: Visit 2 and Visit 1 can be combined to start Pump Therapy in Manual Mode + SBL.

- Train subject and parent(s)/guardian(s) on the MiniMed 780G system
- Train the subject and parent(s)/guardian(s) on the use of pump therapy in Manual Mode + SBL set at 65 mg/dL (3.6 mmol/L)
- Set-up subject CareLink Account.
- CareLink Training
- Start pump therapy in Manual Mode + SBL
- Collection of sensor site location
- Collection of questionnaires
- Review adverse events or device deficiencies, if any.
- Visit 3 (Office/Remote): End of Run-in & Randomization [Visit 2 + 14 days (Window + 14 days)]
 - Ensure CareLink upload was done
 - Review Pump therapy/adjust settings (see **Table 6**)
 - Retrain subject on 780G system as needed
 - Collection of sensor site location
 - Review adverse events or device deficiencies, if any
 - o Investigator will review randomization criteria

If subject is eligible will be randomized to one of the two sequences:

- Sequence A: start pump therapy in Auto Mode (Treatment)
- Sequence B: continue pump therapy in Manual Mode + SBL set at 65 mg/dL (3.6 mmol/L) (Control)

If subject is not eligible:

 Subject will be withdrawn from the study. All devices and unused consumables will have to be returned to the site.

D00674412

Study Phase:

Sequence A Only:

- Visit 3A** (Office/Remote): Auto Mode Start [Visit 3 +0- 3 days (Window + 2 days max)]
 - ** Note: Visit 3A and Visit 3 can be combined to start pump therapy in Auto Mode
 - \circ $\,$ Train the subject and parent(s)/guardian(s) on the use of pump therapy in Auto Mode
 - Subject to start pump therapy in Auto Mode.
 - Collection of sensor site location
 - Ensure CareLink upload was done
 - Review pump therapy/adjust settings (see **Table 6**).
 - Retrain subject on 780G system as needed.

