 - Review adverse events or device deficiencies, if any.

Sequence A and B:

- Visit 4 (Office/Remote): Follow up visit [Visit 3+14 days (Window ± 5 days)]
 - Ensure CareLink upload was done
 - \circ Collection of sensor site location
 - Review Pump therapy/adjust settings (see **Table 6**).
 - Retrain subject on 780G system as needed.
 - Review adverse events or device deficiencies, if any.
- Visit 5 (Office/Remote): Follow up visit [Visit 3+28 days (Window ± 5 days)]
 - Ensure CareLink upload was done
 - Collection of sensor site location
 - Review Pump therapy/adjust settings (see **Table 6**).
 - Retrain subject on 780G system as needed.
 - \circ $\;$ Review adverse events or device deficiencies, if any.

• Visit 6 (Office/Remote): Follow up visit [Visit 3+56 days (Window ± 5 days)]

- Ensure CareLink upload was done
- Collection of sensor site location
- Review Pump therapy/adjust settings (see **Table 6**).
- Retrain subject on 780G system as needed.
- Review adverse events or device deficiencies, if any.

Visit 7 (Office/Remote): End of Period 1 [Visit 3 + 84 days (Window ± 5 days)]

- Perform blood sample collection for HbA1c at Local Lab.
- $\circ \quad \text{Ensure CareLink upload was done} \\$
- \circ Collection of sensor site location
- Review Pump therapy/adjust settings (see **Table 6**).
- Retrain subject on 780G system as needed
- Measure/Collect height and weight.

CIP342 Clinical Investigation Plan Image: Comparison of the second s

- Collection of questionnaires
- Review adverse events or device deficiencies, if any.

For subjects randomized in Sequence A:

- Stop Auto Mode and start using Pump therapy in Manual Mode with SBL set at 65 mg/dL (3.6 mmol/L).
- Re-train the subject and parent(s)/guardian(s) on the use of pump therapy in Manual Mode as needed
- Visit 8 (Office/Remote): Start of Period 2 [Visit 7 + 14 days (Window + 3 days max)]
 - Ensure CareLink upload was done
 - Collection of sensor site location
 - Review Pump therapy/adjust settings (see **Table 6**).
 - Retrain subject on 780G system therapy as needed.
 - Review adverse events or device deficiencies, if any.

For subjects subject randomized in Sequence B:

- Train the subject and parent(s)/guardian(s) on the use of pump therapy in Auto Mode
- To start Pump therapy in Auto Mode.

Sequence B Only:

- Visit 8A (Office/Remote): Follow up visit [Visit 7 + 28 days (Window ± 5 days)]
 - Ensure CareLink upload was done
 - Collection of sensor site location

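### The period 1 TIR window opens at Visit 3, but sequence A starts Auto Mode only at Visit 3A, so up to 4 (at most 5) Manual Mode days can count as Auto Mode

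*SAP*

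**What the plan says.** **Device windows (SAP 7.2).** Period 1 is defined once, for both sequences: "Study phase period 1: from Visit 3 (excluded) to Visit 7 (excluded"). Period 2 is "Study phase period 2: from Visit 8 (excluded) to Visit 11 (excluded"). The SAP adds that "CGM data from the day of the visits will not be included in the device data metrics calculation", and gives as its reason the avoidance of bias from changes of treatment and settings.

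**Start of Auto Mode (Protocol 9.1).** In sequence A this is Visit 3A: "Auto Mode Start [Visit 3 +0- 3 days (Window + 2 days max"). A note allows that "Visit 3A and Visit 3 can be combined to start pump therapy in Auto Mode". Up to that point the child is in the run-in mode: "During Run-in Phase subject will use 780G system in Manual Mode + SBL set at 65 mg/dL". In sequence B, Auto Mode starts at Visit 8, which is also where the period 2 window is anchored.

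**End of period 1.** The visit schedule in Protocol 9.1 gives "End of Period 1 [Visit 3 + 84 days (Window ± 5 days"). The narrative at the start of the same section instead counts sequence A's Visit 7 as 12 weeks after Auto Mode start.

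**Safety windows (SAP 7.2).** These also open at Visit 3: "Study phase period 1: from Visit 3 (included) to Visit 7 (included"). SAP 7.10 assigns events to periods by the 7.2 rule and reports them both by randomized arm and by treatment actually received.

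In the SAP text available, Visit 3A is mentioned only for children newly enrolled in the continuation phase. No rule moves the start of period 1 for sequence A.

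**The concern.** The study-phase primary endpoint is the Auto minus Manual difference in TIR, tested for non-inferiority at -7.5 points (SAP 7.9.1). Any days between Visit 3 and Visit 3A are control-condition days that the window labels as treatment. The SAP drops visit days to keep treatment changes out of the metric, but it anchors the window on a visit at which sequence A may not yet have changed treatment.

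Mixing control data into the treatment window pulls the estimated difference towards zero. Under a non-inferiority hypothesis this is the unfavourable direction if Auto Mode is worse, because it brings a true deficit closer to zero. Only one of the four sequence-by-period cells is affected. The dilution is therefore halved in the crossover mean but appears in full in the period-1-only analysis that SAP 7.9.1 uses if the sequence term has p ≤ 0.1. The same asymmetry slightly shifts the sequence term that triggers that fallback.

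**Working it through.** The text available gives no power, SD or expected TIR difference for this endpoint, so there is no planned figure to reproduce. The check is of the window arithmetic and what follows from it.

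**Inputs from the documents**
- Maximum lag from Visit 3 to Visit 3A: 3 + 2 = 5 days; minimum 0.
- Period 1 window with Visit 7 on day 84: days 1 to 83 after Visit 3, so 83 days. With Visit 7 at its earliest (day 79): 78 days.
- Allocation 1:1; about 72 study-phase completers; margin -7.5 points; one-sided alpha 0.025.

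**Assumptions**
- Gap days have the child's Manual Mode TIR, and sensor data are spread evenly over days.
- The SD of the paired difference is 6 to 15 points.
- Every sequence A child has the same lag.

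**Share of the window in Manual Mode, f (Visit 7 on day 84)**

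| Lag (days) | Visit 3A day dropped | Visit 3A day kept, counted as Manual |
|---|---|---|
| 0 | 0 | 0 |
| 1 | 0 | 1/83 = 1.2% |
| 3 | 2/82 = 2.4% | 3/83 = 3.6% |
| 5 | 4/82 = 4.9% | 5/83 = 6.0% |

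With Visit 7 on day 79 the largest value is 5/78 = 6.4%.

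**Effect on the estimate.** For a true difference D, sequence A estimates D(1 − f) and sequence B estimates D. The crossover mean is therefore D(1 − f/2), and the period-1-only contrast is D(1 − f). At a 5-day lag:
- Crossover dilution f/2: 2.4% to 3.0%. Period-1-only dilution f: 4.9% to 6.0%.
- D = 10: crossover 9.76 to 9.70; period 1 only 9.51 to 9.40.
- D = -7.5: shift 7.5 × (4/82)/2 = 0.18 to 7.5 × (5/83)/2 = 0.23, so the expected estimate is -7.32 to -7.27.
- Sequence term: shifted by fD/2 in size, which is 0.24 to 0.30 points at D = 10.

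**One-sided error at the margin, crossover analysis.** Error = 1 − Φ(1.96 − 7.5(f/2)/SE), with SE = SD/√72. Example for SD 10 and f = 4/82: SE = 1.179, 0.183/1.179 = 0.155, and 1 − Φ(1.805) = 0.0356.

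| Assumed SD | f = 4/82 | f = 5/83 |
|---|---|---|
| 6 | 0.0444 | 0.0505 |
| 8 | 0.0387 | 0.0427 |
| 10 | 0.0356 | 0.0385 |
| 12 | 0.0336 | 0.0359 |
| 15 | 0.0317 | 0.0335 |

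The extreme corner, f = 5/78 with SD 6, gives 0.0526. The range is therefore about 3.2% to 5.3%, its top value needing Visit 7 on day 79.

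**TIR superiority power at D = 5.** SD 10: 0.989 falls to 0.985 or 0.984 (f = 4/82 or 5/83). SD 15: 0.807 falls to 0.788 or 0.783.

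**The case against.** **The Visit 3 anchor has a rationale.** Randomization is at Visit 3, SAP 7.7.1 starts the study phase there, and the ITT definition in SAP 7.1.3 analyses children under the intended treatment whatever their compliance. Even the per-protocol set tolerates Auto Mode use down to 75%, so a start-up delay of about 5% looks minor. This stands in part: it is a reason to keep the Visit 3 window as a sensitivity analysis. It does not settle the matter. The gap days are not non-compliance; the protocol schedules them before Auto Mode begins. The SAP does not give ITT as the reason for its window, and its visit-day exclusion points the other way. For newly enrolled continuation children, the SAP itself ends run-in 2 at Visit 3A (7.2) and starts period 1 exposure there (7.7.2).

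**The change-over day.** A reader might infer that the Visit 3A day itself contaminates the metric. Visit 3A is a scheduled visit, so the general visit-day rule plausibly removes it. A 5-day lag then leaves 4 full Manual days, and a lag of 0 or 1 day leaves none. The 5-day figures hold only if the rule is applied solely to the visits named in the window list.

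**Safety.** A reader might infer that adverse events before Visit 3A will be wrongly charged to Auto Mode. The by-period tables would place them in sequence A's Auto Mode period, but SAP 7.10 also reports by treatment actually received, and the SAP plans no statistical test on safety endpoints. What remains is a labelling point.

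**Size.** A reader might infer that the non-inferiority conclusion is unreliable. That needs every sequence A child at the maximum lag and a true difference close to -7.5. The documents allow a zero lag, do not say how often the visits are combined, and describe better TIR with this system in older children. If the same holds at ages 2–6 years, the dilution works against the sponsor in both the non-inferiority and the superiority test.

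**Conclusion.** The mismatch is real. The period 1 device window can include control-condition days in sequence A, this runs against the SAP's own stated aim, and nothing in the text available corrects it.

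The effect is small and every figure is an upper bound. It is zero when Visits 3 and 3A are combined. The inflated error applies only at the margin and rests on assumed SDs, a uniform 5-day lag and gap-day TIR equal to Manual Mode TIR. Away from the margin the dilution is unlikely to decide the primary result on its own, and if Auto Mode is better the cost is a slight loss of superiority power.

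It should still be corrected, because it sits in the primary endpoint, favours the sponsor if Auto Mode is worse, doubles as a proportion of the effect in the period-1-only fallback, and is easy to remove.

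**What to change.** 1. **Device window.** In SAP 7.2, for sequence A, define period 1 as Visit 3A (excluded) to Visit 7 (excluded). This mirrors the Visit 8 anchor for sequence B, which stays unchanged. The Manual share f becomes 0 and the expected estimate is D.
2. **Gap days.** Keep Visit 3 to Visit 3A as a separate post-randomization, pre-Auto Mode interval. Do not add it to run-in: that would put post-randomization data into the baseline of one sequence only and contradict SAP 7.7.1, where run-in ends at randomization.
3. **Safety.** Show adverse events in that interval under Manual Mode in the actual-treatment tables.
4. **Sensitivity analysis.** Repeat the primary analysis with the Visit 3 window.
5. **Visit 7 anchor.** Reconcile the Protocol 9.1 narrative, which counts sequence A's Visit 7 from Auto Mode start, with the schedule, which counts it from Visit 3.

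The cost is one SAP line and a small programming change. At the maximum lag with Visit 7 on day 84, the sequence A window falls from 83 to 78 days, so at most 5 days of data are lost.
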